**TABLE F-1: SERIOUS ADVERSE EVENTS THAT REQUIRE EXPEDITED REPORTING BY INDIVIDUAL CASE SAFETY REPORTS (ICSR)**

Adverse Event	Seriousness or Capture Method	Collection Form
ALLERGY/IMMUNOLOGY		
Anaphylactic reaction	SAE	ICSR
CARDIAC		
Asystole	SAE	ICSR
Atrial Ventricular Block	SAE	ICSR
Congestive Heart Failure	SAE	ICSR
Myocardial Infarction	SAE	ICSR
Pericarditis	SAE	ICSR
Pericardial disease	SAE	ICSR
Pericardial effusion (including tamponade)	SAE	ICSR
Prolongation of QTc interval	SAE	ICSR
Sinus Bradycardia	SAE	ICSR
Supraventricular Tachycardia	SAE	ICSR
Ventricular Tachycardia	SAE	ICSR
Pulmonary hypertension	SAE	ICSR
COAGULATION		
Disseminate intravascular coagulation (DIC)	SAE	ICSR
DERMATOLOGY		
Erythema multiforme (toxic epidermal necrolysis)	SAE	ICSR
Sweet's Syndrome (acute neutrophilic dermatosis)	SAE	ICSR

Adverse Event	Seriousness or Capture Method	Collection Form
Pyoderma gangrenosum	SAE	ICSR
Vasculitis	SAE	ICSR
ENDOCRINE		
Hyperthyroidism	SAE	ICSR
GASTROINTESTINAL		
Ileus (functional obstruction of bowel, i.e., neuroconstipation)	SAE	ICSR
GI Perforation	SAE	ICSR
Diverticulitis	SAE	ICSR
Ischemic bowel	SAE	ICSR
HEMORRHAGE		
Central Nervous system	SAE	ICSR
HEPATOBIILIARY/PANCREAS		
Liver dysfunction/failure (Clinical - CTCAE)	SAE	ICSR
Pancreatitis	SAE	ICSR
NEUROLOGY		
Neurology – Peripheral neuropathy	SAE	ICSR
Neuropathy: Motor	SAE	ICSR
Neuropathy: Sensory	SAE	ICSR
Syncope (fainting) 	SAE	ICSR
CNS ischemia	SAE	ICSR
Coma	SAE	ICSR
Cranial palsy	SAE	ICSR
Seizure	SAE	ICSR
Spinal cord compression	SAE	ICSR
Brain Edema	SAE	ICSR
Encephalopathy	SAE	ICSR
Leukoencephalopathy syndrome including reversible posterior leukoencephalopathy syndrome [RPLS]) or (Leukoencephalopathy radiographic findings)	SAE	ICSR
PULMONARY/UPPER RESPIRATORY		
Acute Respiratory Distress Syndrome	SAE	ICSR
Alveolar Hemorrhage	SAE	ICSR
Pleural effusion (non-malignant)	SAE	ICSR
Pneumonitis/Pulmonary Infiltrates (absence of infection)	SAE	ICSR
Pulmonary Hypertension	SAE	ICSR

Adverse Event	Seriousness or Capture Method 	Collection Form
RENAL/GENITOURINARY		
Renal failure	SAE	ICSR
SYNDROMES		
Tumor flare	SAE	ICSR
Tumor lysis syndrome	SAE	ICSR
VASCULAR		
Acute vascular leak syndrome	SAE	ICSR
DEATH		
Sudden death	SAE	ICSR
OTHER		
Second malignancies	SAE	ICSR

 Serious Adverse events are defined by the 21 CFR (312.32a): AE that results in death, requires hospitalization, persistent or significant disability or incapacity, congenital anomaly, that is life threatening or considered as medically important.

**TABLE F-2: EXPECTED ADVERSE EVENTS OF INTEREST THAT WILL REQUIRE EXPEDITED REPORTING IF THEY MEET SERIOUS ADVERSE EVENT CRITERIA AND OCCUR AFTER THE INITIATION OF LENALIDOMIDE AND THROUGH 28 DAYS AFTER THE DISCONTINUATION OF LENALIDOMIDE**

Adverse Event	Seriousness or Capture Method 	Collection Form
AUDITORY/EAR		
Hearing loss	SAE	ICSR
CARDIAC		
Atrial fibrillation	SAE	ICSR
Atrial flutter	SAE	ICSR
COAGULATION		
Deep vein thrombosis	SAE	ICSR
Pulmonary emboli 	SAE	ICSR
HEMORRHAGE		
Hemorrhage, Gastrointestinal	SAE	ICSR
Hemorrhage, Pulmonary	SAE	ICSR
METABOLIC/LABORATORY		
Elevation of ALT $\geq 2.5x$ ULN	SAE	ICSR
Elevation of AST $\geq 2.5x$ ULN	SAE	ICSR
Elevation of Bilirubin $\geq 3x$ ULN	SAE	ICSR
MUSCULOSCELETAL/SOFT TISSUE		
Muscular weakness	SAE	ICSR
NEUROLOGY		
Neurology – Peripheral neuropathy	SAE	ICSR

Adverse Event	Seriousness or Capture Method	Collection Form
Neuropathy: Motor	SAE	ICSR
Neuropathy: Sensory	SAE	ICSR
Syncope (fainting)	SAE	ICSR
OCULAR/VISUAL		
Vision – Blurred vision	SAE	ICSR
PAIN		
Pain – Neuralgia	SAE	ICSR
INFECTION		
Febrile neutropenia	SAE	ICSR
DEATH		
Sudden death	SAE	ICSR
OTHER		
Second malignancies	SAE	ICSR

 Serious Adverse events as defined by the 21 CFR (312.32a): AE that results in death, requires hospitalization, persistent or significant disability or incapacity, congenital anomaly, that is life threatening or considered as medically important.

1.1 Study Objectives

BMT CTN protocol 07LT is a follow-up study to BMT CTN 0702, which was a Phase 3, multicenter trial designed to compare progression-free survival and additional outcomes between patients randomized to one of three treatment arms:

- Autologous transplant followed by a second autologous transplant then maintenance therapy (Auto/Auto)
- Autologous transplant followed by consolidation therapy with lenalidomide (Revlimid), bortezomib (Velcade) and dexamethasone (RVD) then followed by maintenance therapy (Auto/RVD)
- A single autologous transplant followed by maintenance therapy (Auto/Maint)

1.1.1 Primary Objective

The primary objective of the study is to compare progression-free survival (PFS) as a time to event analysis between the three randomized treatment arms from the BMT CTN 0702 protocol as a pairwise comparison. The analysis will be conducted once all alive patients have been enrolled for 5 years post randomization on the BMT CNT 0702 protocol.

1.1.2 Secondary Objectives

The secondary objectives of the study are:

- Cumulative incidence of second primary malignancies (SPM)
- Probability of overall survival (OS)
- Probability of event-free survival (EFS)
- Health Quality of Life (QOL)

1.2 Study Design and Procedures

1.2.1 Primary Hypothesis and Primary Endpoint

The primary hypothesis of this study and the original BMT CTN 0702 study is that the use of novel anti-myeloma agents will improve long-term PFS after high-dose melphalan followed by autologous hematopoietic cell transplantation (HCT) as compared to a second autologous transplantation.

To correspond with the primary objective to compare progression-free survival (PFS) as a time to event analysis between the three randomized treatment arms from the BMT CTN 0702

protocol as a pairwise comparison, the main null and alternative hypotheses of the study are that the different treatment arms will have different rates of long-term PFS:

H₀₁: PFS_{Auto/Auto} = PFS_{Auto/RVD}
H_{A1}: PFS_{Auto/Auto} ≠ PFS_{Auto/RVD}

H₀₁: PFS_{Auto/Auto} = PFS_{Auto/Maint}
H_{A1}: PFS_{Auto/Auto} ≠ PFS_{Auto/Maint}

Ho1: PFSAuto/RVD = PFSAuto/ Maint Ha1: PFSAuto/RVD ≠ PFSAuto/ Maint

These three hypotheses will each be tested with a two-sided stratified log rank test at the α =0.05 / 3 level using a Bonferroni correction to control the overall type I error rate.

The primary endpoint is PFS. Patients are considered a failure of the primary endpoint if they die or suffer from disease progression. The time to this event is the time from randomization on the BMT CTN 0702 protocol until progression, death, or initiation of non-protocol anti-myeloma therapy, or until last myeloma follow-up through December 2018 if there is no event.

1.2.2 Accrual Plan and Randomization

Participants were eligible to accrue on to BMT CTN 07LT as soon as they finished the earlier of 3 years of maintenance therapy on BMT CTN 0702 or four years of follow up on BMT CTN 0702. The protocol was approved after some participants had already finished 3 years of maintenance on BMT CTN 0702 so they were eligible to enroll when the protocol was activated, and there may have been a period when the participant was on commercially-available lenalidomide or other treatment. The protocol was activated in March 2015, and accrual was targeted through the beginning of 2018 to allow a window of time after the last person enrolled on BMT CTN 0702 would be eligible for BMT CTN 07LT.

Randomization occurred on the parent BMT CTN 0702 trial, which had a 1:1:1 randomization ratio with permuted blocks. Randomization on the parent trial was also stratified by patient risk and center. There was no additional randomization on BMT CTN 07LT.

1.2.3 Duration of Follow-up

Participants will be followed for until death, progression, withdrawal from study, or the end of 2018. The randomization date on the BMT CTN 0702 trial will be the start time for most of the analyses, except for the secondary analysis of PFS which starts at initiation of maintenance therapy and includes discontinuation of lenalidomide as a time-varying covariate.

1.3 Inclusion and Exclusion Criteria

As a follow-on study, the 07LT protocol is open for enrollment of participants randomized on 0702 who have completed 3 years of maintenance therapy on 0702 or 4 years of follow-up on 0702, have not died or had clinical progression, and have signed the 07LT informed consent form.

Participants who have completed 3 years of maintenance therapy on BMT CTN 0702 are eligible for continued maintenance therapy on 07LT if they are willing and able to comply with the requirements of the Revlimid REMS® program, and have signed an informed consent. Participants who are pregnant, breastfeeding, unwilling to take DVT prophylaxis, had thromboembolic events while on full anticoagulation during lenalidomide use, or had secondary primary malignancies after initiation of lenalidomide on BMT CTN 0702 are ineligible for initiating BMT CTN 07LT maintenance therapy.

1.4 Treatment Description

Lenalidomide will be administered initially at the patient's last documented dose prior to discontinuation of BMT CTN 0702 lenalidomide maintenance therapy. Cycle duration is 28 days. Patients will continue lenalidomide until disease progression, or discontinuation due to toxicity, death, or withdrawal from the study. Patients who discontinue lenalidomide due to any reason other than death or withdrawal of consent will continue to be followed.

In the presence of lenalidomide-related non-hematologic toxicities, the study drug will be withheld until the toxicity resolves, then restarted at a reduced dose as described in the protocol. Dose modifications for hematologic toxicities are described in the protocol. If the patient is on DVT/PE prophylaxis or treatment, discontinuation or modifications of anticoagulation should be considered by the treating physician.

If a dose reduction has occurred and ANC \geq 1000/µL and platelet count is \geq 75,000/µL, the study drug dose may be re-escalated as shown in the protocol, one step per cycle to a maximum of 15 mg daily.

1.5 Response Variables and Data Collection Time Points

Participants are evaluated for the primary endpoint of progression-free survival (death, disease progression, initiation of non-protocol myeloma therapy) and for the following secondary endpoints:

- Overall survival
- Event-free survival (no progression, death, or SPM)
- Incidence of SPM
- Unexpected grades 3-5 adverse events
- Health quality of life

Patients have visits every six months until death, progression, withdrawal of consent, or the end of the study.

Participants who receive long-term lenalidomide maintenance therapy are required to report unexpected grades 3-5 adverse events until the patient progresses or until 28 days from their last dose of lenalidomide. These require expedited reporting within 24 hours – 3 business days of the site's knowledge of the event, depending on the type of event. The protocol specifies additional rules for reporting requirements of AEs after an SPM depending on the treatment received for the SPM, and for reporting serious expected adverse events and selected AEs of interest.

Participants who do not receive lenalidomide maintenance or have permanently discontinued lenalidomide maintenance not required to report adverse events except for SPMs.

For all participants on 07LT, SPMs must be reported within three business days of knowledge of the event and deaths must be reported within 24 hours of knowledge of the participant's death. Non-melanoma skin cancers are not required to be reported.

Health quality of life surveys are completed at visits corresponding to 5, 6, and 7 years from original randomization on 0702.

2. General Statistical Considerations

Unless stated otherwise:

- For continuous outcomes, descriptive statistics will include the number of subjects (n), mean, standard deviation, median, minimum and maximum.
- For categorical outcomes, frequencies and percentages will be displayed for categorical data.
- All statistical comparisons made using 2-sided pairwise tests will be compared to an α =0.05/3 significance level.

2.1 Sample Size and Power Calculations

The projected sample size for this study was determined from the available sample size of the parent study, BMT CTN 0702, and the rate of progression-free survival on 0702. Seven hundred and fifty-eight participants enrolled on 0702, and it was anticipated that the sample size on 07LT could range from 417 to 569 for 3-year PFS ranging from 55% to 75%.

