## PROTOCOL SYNOPSIS – BMT CTN 0702 LONG-TERM FOLLOW-UP PROTOCOL

### Continued, Long-Term Follow-Up and Lenalidomide Maintenance Therapy for Patients Who Have Enrolled on BMT CTN 0702

- Co-Principal Investigators:** [name], [name], and [name]
- Study Design:** The study is designed to provide continued, long-term follow-up on patients enrolled on BMT CTN 0702 who have not experienced progression, as well as to offer optional long-term lenalidomide maintenance therapy to those BMT CTN 0702 patients who have completed 3 years of protocol-defined maintenance therapy without evidence of disease progression.
- Primary Objective:** The primary objective is to compare progression-free survival (PFS) as a time to event analysis between the three randomized treatment arms from the BMT CTN 0702 protocol as a pairwise comparison. The analysis will be conducted once all surviving patients have been followed for at least 5-years post randomization on the BMT CTN 0702 protocol.
- Secondary Objectives:** Secondary objectives include the cumulative incidence of second primary malignancies (SPM), probability of overall survival (OS), probability of event-free survival (EFS) and Health Quality of Life (QOL) on all patients, including those not receiving long-term lenalidomide maintenance therapy.
- Eligibility Criteria:** Patients eligible for long-term follow-up are those who were enrolled and randomized on the BMT CTN 0702 protocol and who are alive at the end of the BMT CTN 0702 protocol-defined follow-up period without progression. Patients eligible for long-term lenalidomide maintenance therapy include patients who have completed 3 years of BMT CTN 0702 protocol-defined lenalidomide maintenance therapy with no evidence of disease progression.
- Treatment/Follow-Up:** All patients who consent to the long-term follow-up protocol will undergo study assessments every 6-months. Patients eligible to continue with lenalidomide maintenance therapy will continue with the last tolerated dose of lenalidomide that was documented upon completion of BMT CTN 0702 maintenance therapy.

[figure not shown]
**Accrual Objective:** It is anticipated that approximately 450 patients will be enrolled on this protocol based on assumed estimates of PFS from the BMT CTN 0702 study. The total sample size may be as low as 417 if the observed 3-year PFS on the BMT CTN 0702 is 55% but may be as high as 569 if the 3-year PFS is 75%.

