### 1. BACKGROUND AND RATIONALE

#### 1.1. Background

Therapeutic advances in multiple myeloma (MM) have resulted in substantially improved survival. Similarly, in a large population-based study of 45,595 MM patients, myeloma-specific 5-year median overall survival (OS) improved from 36% to 68% under age 50, and from 34% to 58% among patients of ages 51-65 years between 1973 and 2009.

Post-transplant consolidation and maintenance strategies have also yielded improved progression-free survival (PFS) and OS. The BMT CTN 0702 study randomized patients to receive two autologous hematopoietic cell transplants (HCT), or one autologous HCT and post transplant consolidation, or one autologous HCT with maintenance. Of note, all patients receive a total of 3 years of maintenance therapy using lenalidomide. Since the implementation of BMT CTN 0702, the experience with maintenance has broadened, and at least two large phase III clinical trials that continued lenalidomide maintenance for longer periods were associated with longer survival, compared to placebo. This long-term follow-up protocol focuses on extending the follow-up period for all patients on BMT CTN 0702 to assess long-term outcomes such as PFS and incidence of SPMs. A secondary objective is to provide patients with lenalidomide maintenance therapy free of charge until there is evidence of disease progression.

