#### **2.3.1. Initial Patient Eligibility Criteria for Long-Term Follow-Up Only**

Patients fulfilling the following criteria will be eligible to provide continued long-term follow-up data as part of this study:

1. Enrolled and randomized on the BMT CTN 0702 protocol
2. Alive at the completion of BMT CTN 0702 protocol specified follow-up defined as 4 years post-randomization
3. Patients without evidence of disease progression at the completion of BMT CTN 0702 protocol specified follow up. (see Section 3.1 for disease progression definition)
4. Signed Informed Consent Form
5. Patients with the ability to speak English or Spanish are eligible to participate in the HQL component of this trial.

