#### **2.3.2. Patient Eligibility Criteria for Optional Long-term Lenalidomide Maintenance Therapy**

Patients fulfilling the following criteria will be eligible to provide continued long-term follow-up data AND receive long-term lenalidomide maintenance therapy as part of this study:

1. Enrolled and randomized to BMT CTN 0702
2. Completion of 3 years of maintenance therapy on BMT CTN 0702
3. Registered in the mandatory Revlimid REMS® program (formerly the RevAssist® for Study Participants (RASP) program), and be willing and able to comply with the requirements of the Revlimid REMS® program, including counseling, pregnancy testing, and phone surveys.
4. Signed informed consent form.
5. Patients with the ability to speak English or Spanish are eligible to participate in the HQL component of this trial.

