#### **2.3.3. Patient Exclusion Criteria for Long-term Lenalidomide Maintenance Therapy**

Patients who meet any of the following criteria will be ineligible to receive long-term lenalidomide maintenance therapy as part of this study\*:

1. Patients who have evidence of disease progression prior to enrollment (see Section 3.1 for disease progression definition).

---

\* All patients will be followed for long-term outcomes.

2. Patients who were discontinued from BMT CTN 0702 lenalidomide maintenance therapy, for any reason, prior to the completion of the 3 years of 0702 maintenance.
3. Female patients who are pregnant (positive -BetaHCG) or breastfeeding.
4. Females of childbearing potential (FCBP) or men who have sexual contact with FCBP unwilling to use contraceptive techniques (Appendix B) during the length of lenalidomide maintenance therapy.
5. Patients who experienced thromboembolic events while on full anticoagulation during prior therapy with lenalidomide.
6. Patients unwilling to take DVT prophylaxis.
7. Patients who developed a second primary malignancy, excluding non-melanoma skin cancers after initiation of lenalidomide maintenance therapy on BMT CTN 0702.

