#### 5.2. Accrual, Registration and Follow-up

It is anticipated that approximately 450 patients will be enrolled on this protocol based on assumed estimates of PFS estimates from the BMT CTN 0702 study. The total sample size may as low as 417 if the observed 3-year PFS on the BMT CTN 0702 is 55% but may be as high as 569 if the 3-year PFS is 75%. Follow-up on this protocol will continue through December 31, 2018.

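### Does the 07LT enrolment projection of 417 to 569 need correcting because it assumes that every patient progression-free at 3 years enrols?

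*SAP*

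**What the plan says.** SAP 2.1 states that the projection rests on the parent trial's sample size and its PFS rate, and that "it was anticipated that the sample size on 07LT could range from 417 to 569 for 3-year PFS ranging from 55% to 75" per cent. It names no other factor.

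The Protocol Synopsis words the lower end as "The total sample size may be as low as 417 if the observed 3-year PFS on the BMT CTN 0702 is 55" per cent, with 569 as the high figure at 75%. Protocol 5.2 repeats this with a word dropped: "The total sample size may as low as 417 if the observed 3-year PFS on the BMT CTN 0702 is 55" per cent. Both places also give an accrual objective of about 450, without a derivation.

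There are two entry routes. Follow-up only (Protocol 2.3.1) requires a patient to be progression-free and "Alive at the completion of BMT CTN 0702 protocol specified follow-up defined as 4 years post-randomization". Long-term lenalidomide (Protocol 2.3.2) requires "Completion of 3 years of maintenance therapy on BMT CTN 0702", and Protocol 2.3.3 bars from that route anyone who stopped "for any reason, prior to the completion of the 3 years of 0702 maintenance". SAP 1.2.2 lets patients enter at whichever comes first, 3 years of maintenance or 4 years of follow-up. Both routes need signed consent, and Protocol 5.1 says how patients who decline will be followed.

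**The concern.** The two ends look like a low and a high forecast, but both are the 3-year progression-free count with nobody lost. The documents' own rules push enrolment below that count:

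- Follow-up-only entry comes a year after the time point used.
- Maintenance follows one or two transplants, so 3 years of maintenance ends more than 3 years after randomization if randomization precedes transplant. The order of events in Protocol 1.1 and SAP Exhibit 07LT-1 suggests that it does.
- Some patients had finished maintenance before 07LT opened (SAP 1.2.2).
- Consent can be refused.

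On that reading, the lower figure is nearer to a ceiling for the 55% scenario than to a floor. At stake would be the size of the adverse-event tables and quality-of-life summaries, which use 07LT enrollees only. It would also affect how many progression-free patients have late progression reported through CIBMTR instead of at 6-monthly protocol visits.

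**Working it through.** **Inputs.** N = 758 and 3-year PFS of 55% to 75% (SAP 2.1); entry at 4 years, or after 3 years of maintenance (Protocol 2.3.1 and 2.3.2; SAP 1.2.2). The documents give no enrolment rate and no shape for the PFS curve, so both are assumed below.

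**Reproducing the plan.** N × PFS at 3 years:

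- 758 × 0.55 = 416.9, rounded up to 417
- 758 × 0.75 = 568.5, rounded up to 569

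The implied enrolment fractions are 417/416.9 = 1.000 and 569/568.5 = 1.001, so the only departure from full enrolment is rounding.

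**Moving the entry time.** Under an assumed constant hazard, PFS at m months is PFS(36)^(m/36).

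- 38 months (assumed, for early completers of maintenance): 0.55^(38/36) = 0.5320, giving 403.3; 0.75^(38/36) = 0.7381, giving 559.5
- 48 months: 0.55^(48/36) = 0.4506, giving 341.6; 0.75^(48/36) = 0.6814, giving 516.5

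| Entry time | Full enrolment | 90% (assumed) | 80% (assumed) |
|---|---|---|---|
| 36 months (as in the plan) | 416.9 to 568.5 | 375 to 512 | 334 to 455 |
| 38 months | 403.3 to 559.5 | 363 to 504 | 323 to 448 |
| 48 months | 341.6 to 516.5 | 307 to 465 | 273 to 413 |

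With all entry at 48 months and full enrolment, the ends fall by 1 − 341.6/416.9 = 18% and 1 − 516.5/568.5 = 9%. Weibull shapes of 0.8 and 1.2 instead of constant hazard move the 48-month lower end to 357 and 326.

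**The accrual objective of 450.** As a share of the 3-year pool:

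- PFS 55%: 450/416.9 = 108%, which is impossible
- PFS 65%: 450/492.7 = 91%, leaving about 43 not enrolled
- PFS 75%: 450/568.5 = 79%, leaving about 119 not enrolled

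So 450 is compatible with incomplete enrolment in the middle and upper part of the PFS range.

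**What depends on the projection.**

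- Power: SAP 2.1 contains no power calculation.
- PFS, overall survival, event-free survival and second malignancies: all 758 randomized patients (SAP 2.2 and 2.7.1).
- Adverse events: tabulations; the shells in Exhibits 07LT-9A and 9B have no test column.
- Quality of life: descriptive, with no formal testing (SAP 4.2).

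**The case for a change.** The strongest case for acting is that a reader judging how complete late PFS follow-up will be is given too favourable a picture, and that relabelling the range costs one sentence. The core of this stands: no scenario allows for refusal or for events between year 3 and entry.

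Four points limit it.

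- The figures are conditional on PFS. Both documents give 417 for 55% and 569 for 75%, which are the ends across PFS scenarios. Neither is offered as a guaranteed minimum within a scenario, and both are computed correctly.
- The pool is not a strict ceiling. Starting non-protocol myeloma therapy is a PFS event (Protocol 5.3, SAP 4.1), but only death and progression bar follow-up entry (Protocol 2.3.1, SAP 1.3). A few patients with a PFS event could therefore enrol, and observed counts vary around their expectation.
- Non-enrolment is already planned for. CIBMTR data are combined with parent-trial data (SAP 2.2), and there is a censoring rule for patients who did not enrol (SAP 4.1). Reasons for not enrolling are tabulated (Exhibit 07LT-1), and time to last contact is shown separately for those enrolled and not enrolled (Supplemental Exhibit 07LT-1).
- The 4-year entry in Protocol 2.3.1 and the earlier-of rule in SAP 1.2.2 are largely one route and the union of two routes. Patients who stopped maintenance early lose only the lenalidomide route; they can still enter at 4 years.

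**Conclusion.** No change is needed. The range is the expected 3-year progression-free count with full enrolment, so each end is approximately the maximum for its PFS scenario. Actual enrolment would probably be lower: by 18% and 9% if all entry were at 4 years under constant hazard, and by more with incomplete consent. Those sizes rest on an assumed curve and assumed enrolment rates.

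This is an unstated planning assumption that analysts can read off from 758 × PFS. No power figure, significance threshold or analysis uses it, and the time-to-event comparisons keep all 758 patients whatever the enrolment. SAP 2.1 also reports it as a past expectation, for a study activated in March 2015 with accrual targeted through the beginning of 2018 (SAP 1.2.2). A note saying that the range assumes full enrolment, and where 450 comes from, would be harmless. It would alter no result, and without an enrolment rate in the documents it could not supply a better number.
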